3.2. Endpoints

3.2.1. *Safety & Efficacy Endpoints:*

Primary:

- Long term safety of rVA576 (Coversin) therapy as assessed by AEs, serious adverse events (SAEs), vital signs, results of standard laboratory tests (clinical chemistry, haematology and urinalysis), and results of electrocardiograms (ECGs).

PNH Secondary:

1. Proportion of subjects with thrombotic and haemolytic event-free status during each 3 month time period since the start of the study.
2. Time to thrombotic or haemolytic event since the start of the study.
3. Proportion of subjects who require PRBC transfusion during each 3-month period since the start of the study and over the entire period of the study, with analysis of i) subjects who were transfusion-dependent when they started receiving rVA576 (Coversin), ii) subjects who were transfusion-independent when they started receiving rVA576 (Coversin), and iii) all subjects, and further stratification of these proportions by a) patients who were complement inhibitor-naïve prior to treatment with rVA576 (Coversin), and b) patients who received treatment with another complement inhibitor before switching to rVA576 (Coversin).
4. Time to first transfusion since joining the study.
5. Proportion of subjects with no adverse change in overall scores of Quality of Life using the EORTC QLQ-C30, the EQ-5D-5L and FACIT-F instruments at each 3-month time period since the start of the study.
6. Proportion of subjects with serum Lactate Dehydrogenase (LDH) ≤ 1.8 , >1.8 to 2.4, >2.4 to 3, and >3 times the upper limit of normal (ULN) at each 3-month time period since the start of the study.

7. Proportion of subjects with median serum Lactate Dehydrogenase (LDH) ≤ 1.8 , >1.8 to 2.4 , >2.4 to 3 , and >3 times the upper limit of normal (ULN) over the entire duration of the study.
8. Proportion of transfusion-independent subjects at each 3-month time point, with haemoglobin (g/L) above the baseline haemoglobin value they had at the start of the trial from which they entered CONSERVE. With baseline for CAPSTONE (AK580) defined as the haemoglobin value at which they received their qualifying transfusion (the set point) or for COBALT (AK579) and CONSENT (AK578) the haemoglobin value at which patients entered those trials. With separate analysis of subjects who were i) transfusion-independent prior to receiving rVA576 (Coversin) and remain transfusion-independent and ii) transfusion-dependent prior to receiving rVA576 (Coversin).

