2.4.2 Secondary Endpoints

1. Proportion of subjects with thrombotic and haemolytic event-free status during each 3 month time period since the start of the study.
2. Time to thrombotic or haemolytic event since the start of the study.
3. Proportion of subjects who require PRBC transfusion during each 3-month period since the start of the study and over the entire period of the study, with analysis of i) subjects who were transfusion-dependent when they started receiving rVA576 (Coversin), ii) subjects who were transfusion-independent when they started receiving rVA576 (Coversin), and iii) all subjects, and further stratification of these proportions by a) patients who were complement inhibitor-naïve prior to treatment with rVA576 (Coversin), and b) patients who received treatment with another complement inhibitor before switching to rVA576 (Coversin).
4. Time to first transfusion since joining the study.
5. Proportion of subjects with no adverse change in overall scores of Quality of Life using the EORTC QLQ-C30, the EQ-5D-5L and FACIT-F instruments at each 3-month time period since the start of the study.
6. Proportion of subjects with serum Lactate Dehydrogenase (LDH) <1.8, >1.8 to 2.4, >2.4 to 3, and >3 times the upper limit of normal (ULN) at each 3-month time period since the start of the study.
7. Proportion of subjects with median serum Lactate Dehydrogenase (LDH) <1.8, >1.8 to 2.4, >2.4 to 3, and >3 times the upper limit of normal (ULN) over the entire duration of the study.
8. Proportion of transfusion-independent subjects at each 3-month time point, with haemoglobin (g/L) above the baseline haemoglobin value they had at the start of the trial from which they entered CONSERVE. With baseline for CAPSTONE (AK580) defined as the haemoglobin value at which they received their qualifying transfusion (the set point) or for COBALT (AK579) and CONSENT (AK578) the haemoglobin value at which patients entered those trials. With separate analysis of subjects who were i) transfusion-independent prior to receiving rVA576 (Coversin) and remain transfusion-independent and ii) transfusion-dependent prior to receiving rVA576 (Coversin).

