9. Proportion of transfusion-independent subjects over the entire duration of the study with mean haemoglobin (g/L) above the baseline haemoglobin value they had at the start of the trial from which they entered CONSERVE. With baseline haemoglobin defined as for the previous secondary endpoint (#8). With separate analysis of subjects who were i) transfusion-independent prior to receiving rVA576 (Coversin) and remain transfusion-independent and ii) transfusion-dependent prior to receiving rVA576 (Coversin).

10. Proportion of patients experiencing Major Adverse Vascular Events (MAVE) over the entire period of the study.
11. Time to first Major Adverse Vascular Event (MAVE) for each subject since joining the study.
12. Number of Major Adverse Vascular Events (MAVE) over the entire period of the study.

2.5 Additional Endpoints:

PK and PD parameters during treatment, to include terminal complement activity measured by CH50 ELISA, unbound nomacopan concentration measured by ELISA and total C5 concentration measured by ELISA.

3 Efficacy and Safety Variables

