3.3 Efficacy Measurements and Variables

3.3.1 Blood transfusions

Details of blood transfusions administered during the study will be captured at all visits. Infusion type (PRBC or platelet), date, volume, reason and whether the transfusion was used as a method of PNH treatment will be recorded.

Patients who were transfusion-independent when they started receiving rVA576 (Coversin) and remain transfusion-independent will be identified.

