4.11.3 Transfusion-independence and Haemoglobin

The proportion of transfusion-independent subjects with haemoglobin (g/L) above the baseline haemoglobin value as defined in section 3.3.4 will be summarised at each 3-month time point.

The proportion of transfusion-independent subjects over the entire duration of the study with mean haemoglobin (g/L) above the baseline haemoglobin value as defined in section 3.3.4 will be summarised.

These summaries will be repeated separately for patients :

- i) transfusion-independent prior to receiving rVA576 (Coversin) and remain transfusion-independent
- ii) transfusion-dependent prior to receiving rVA576 (Coversin).

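### As naturally read, haemoglobin endpoints 8 and 9 drop transfused patients from the denominator, so the proportion is biased upward and can stay high or rise while the effect is being lost.

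*Protocol*

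**What the plan says.** Endpoint 8 (Protocol 3.2.1, PNH secondary) is the "Proportion of transfusion-independent subjects at each 3-month time point, with haemoglobin (g/L) above the baseline haemoglobin value". Endpoint 9 is the "Proportion of transfusion-independent subjects over the entire duration of the study with mean haemoglobin (g/L) above the baseline haemoglobin value" (SAP 2.4.2; the protocol has the same endpoint). SAP 4.11.3 plans the first as "The proportion of transfusion-independent subjects with haemoglobin (g/L) above the baseline haemoglobin value as defined in section 3.3.4". Neighbouring endpoints such as 1, 3 and 6 refer simply to subjects, without this restriction.

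The reference value depends on the parent trial. The protocol says "With baseline for CAPSTONE (AK580) defined as the haemoglobin value at which they received their qualifying transfusion (the set point", but "for COBALT (AK579) and CONSENT (AK578) the haemoglobin value at which patients entered those trials". All parent trials are pooled in one proportion, and no split by parent trial is planned.

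Separate summaries are planned for subgroup i, "transfusion-independent prior to receiving rVA576 (Coversin) and remain transfusion-independent", and subgroup ii, patients who were transfusion-dependent before rVA576. SAP 3.3.1 adds: "Patients who were transfusion-independent when they started receiving rVA576 (Coversin) and remain transfusion-independent will be identified".

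Neither document states the denominator, gives a time window for transfusion-independence at a 3-month point, or says how a patient transfused in CONSERVE is counted. SAP 3.2.4 classifies transfusion status only at the start of rVA576. For the haemoglobin baseline SAP 4.11.3 points to section 3.3.4, which is the EORTC QLQ-C30; the definitions are in 3.1 and 3.4.4.

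**The concern.** Remaining transfusion-independent is itself an outcome of treatment. If it defines who is counted, the patients in whom control is lost are the ones removed, and they are not recorded as failures. Subgroup i does this openly, because it keeps only patients who stayed independent. Subgroup ii carries no such condition, so the two rows are not comparable.

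Two other rules can push the same way. Protocol 9.1 leaves missing data out of percentage denominators. SAP 4.2.2 analyses efficacy in patients who reach each time point, while Protocol 5.4.3 and 6.2 allow withdrawal for lack of efficacy or inadequate response.

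Protocol 3.1 gives as one aim of the trial to show that the parent-trial effect is maintained. With no formal inference planned, the reported proportion is the result. A figure that can improve as patients fail works against that aim.

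**Working it through.** The plan states no expected proportion, haemoglobin distribution, set-point value or transfusion trigger, so there is no figure of its own to reproduce. The check is arithmetic on assumed inputs.

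**Inputs.** N = 50 is the approximate planned number (Protocol 9.2). The rest are assumptions:
- L: patients who lose control, i.e. fall to or below their reference haemoglobin
- t: share of those L who are transfused and so leave the transfusion-independent group
- h: share of the other patients whose haemoglobin is above reference

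**Formulas.**
- Planned (restricted) proportion = (N − L)h / [(N − L) + L(1 − t)]
- All-patient proportion = (N − L)h / N

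The numerators are the same and the restricted denominator is never larger, so the restricted figure can never be below the all-patient one.

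**Results with h = 1:**

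| L | All patients | t = 0 | t = 0.5 | t = 0.8 | t = 1 |
|---|---|---|---|---|---|
| 0 | 100% | 100% | 100% | 100% | 100% |
| 5 | 90% | 90% | 94.7% | 97.8% | 100% |
| 10 | 80% | 80% | 88.9% | 95.2% | 100% |
| 20 | 60% | 60% | 75.0% | 88.2% | 100% |
| 30 | 40% | 40% | 57.1% | 76.9% | 100% |

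For L = 20: all patients 30/50 = 60%; restricted 30/(30 + 10) = 75%, 30/(30 + 4) = 88.2% and 30/30 = 100%. With h = 0.9 the same row becomes 27/50 = 54% against 67.5%, 79.4% and 90%.

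**The figure can rise as patients fail.** Assume 20 patients. At month 3, 16 are independent and 15 of them above baseline; at month 24, 8 are independent and all 8 above. The restricted figure goes from 15/16 = 93.8% to 8/8 = 100%. Over all 20 it goes from 75% to 40%.

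**Mix of parent trials (L = 20, h = 1, every CAPSTONE loss transfused).**
- Half of the losses in CAPSTONE patients, 25% to 75% of the other 10 transfused: 30/37.5 = 80.0% to 30/32.5 = 92.3%
- No CAPSTONE patients, 25% to 75% of the 20 transfused: 30/45 = 66.7% to 30/35 = 85.7%
- All-patient figure in every case: 60%

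**How closely transfusion follows the set point.** Haemoglobin minus set point was simulated as normal with SD 12 g/L, its mean falling from 20 to 0 g/L (all assumed):

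| Transfusion occurs | Restricted | All patients |
|---|---|---|
| Exactly at the set point | 100% throughout | 95.2% to 50.1% |
| Around the set point, SD 5 g/L | 98.8% to 87.4% | 92.8% to 43.7% |
| 10 g/L below the set point | 95.8% to 62.8% | 95.2% to 50.1% |

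The upward bias appears in every row; its size depends on transfusion practice that the documents do not describe.

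**The case against.** **The denominator is not stated.** The planned tables pair transfusion-independence with haemoglobin in the FAS, and the FAS is all enrolled patients. One could read both conditions as belonging in the numerator, in which case the main remedy is already in place. This reading is open but less natural, given that neighbouring endpoints say only subjects. It does not rescue subgroup i, which selects on success during follow-up under either reading.

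**Loss of effect shows elsewhere.** Endpoint 3 gives the proportion transfused, including all subjects, and endpoint 4 the time to first transfusion. Table 14.2.1.4 summarises transfusion-independence, and the haematology table gives haemoglobin by visit without restriction. This stands: a reader of the whole report would see the transfusions. But none of these reports haemoglobin and transfusion status jointly, and none corrects 8 and 9.

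**Leaving out transfused patients has a purpose.** Transfusion raises haemoglobin. That is a fair reason not to count such a patient as a success, but not a reason to remove the patient from the count.

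**A stronger reading is tempting.** Because the CAPSTONE reference is the patient's own transfusion set point, a reader might infer that the proportion must sit near 100%, or that these endpoints cannot show loss of effect at all. The documents do not support that. No visible text ties transfusion in CONSERVE to the set point. COBALT and CONSENT patients are compared with entry haemoglobin, and they can fall below it untransfused. The parent-trial mix is unknown. A loss without transfusion would still lower the figure.

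**Conclusion.** The point holds as an upward bias on the natural reading, and as an undefined denominator on any reading. In the 50-patient example with 20 losing control and all others above baseline, the planned figure overstates the all-patient 60% by 15, 28 or 40 percentage points if 50%, 80% or all of the 20 are transfused. There is no overstatement if none is transfused. For CAPSTONE patients the figure could reach 100% regardless of loss, but only if transfusion follows the set point, which is an assumption.

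These are descriptive secondary endpoints under a safety primary, and companion summaries exist. The matter should be corrected, but it does not undermine the trial's main analysis. All counts and transfusion shares above are assumptions; the direction of the bias is not.

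**What to change.** In SAP 4.11.3 and in the wording of endpoints 8 and 9:

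- **Success:** no PRBC transfusion in the 3-month period and haemoglobin above parent trial baseline. For endpoint 9: no PRBC transfusion over the whole study and mean haemoglobin above that baseline. This also supplies the missing time window.
- **Denominator:** all PNH patients in the FAS at that time point. Transfused patients, and patients withdrawn for lack of efficacy or inadequate response, count as not meeting the endpoint. Limiting the count to patients still under observation would let the same selection back in through withdrawal.
- **Subgroup i:** defined by status before rVA576 only, without the requirement to remain independent.
- **Display:** n/N, split by parent trial (CAPSTONE against COBALT/CONSENT), because the reference values differ in kind. The conditional proportion can stay as a supporting line.
- **Cross-reference:** in SAP 4.11.3, change 3.3.4 to 3.1 and 3.4.4.

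**Cost:** revised endpoint wording and four re-programmed tables (14.2.3.1 to 14.2.3.4). No new data are needed, since transfusions, haemoglobin and reasons for withdrawal are already collected. The reported proportions will be lower.

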4.1. Inclusion criteria

- 1) Patients 18 years and above treated with rVA576 (Coversin) under other Akari clinical trial protocols and wish to remain on rVA576 (Coversin) at the conclusion of that trial.
- 2) In the opinion of the treating responsible clinician patient is receiving clinical benefit from continued treatment with study drug.
- 3) Evidence of sustained complement inhibition by CH50 assay.
- 4) Women of childbearing potential (WOCBP) must agree to use effective contraception consistently throughout the study and have a negative pregnancy test at screening. Women are considered post-menopausal and not of childbearing potential if they have had 12 months of amenorrhea and considered sterile if they have had surgical bilateral oophorectomy (with or without hysterectomy) or tubal ligation at least six weeks previously.
- 5) Males with a childbearing potential partner must agree to use effective contraception consistently OR have had a vasectomy.
- 6) Weight ≥ 50 kg.
- 7) Received appropriate prophylaxis against *Neisseria meningitidis* infection, by both immunisation and continuous or intermittent antibiotics.
- 8) The patient is willing to give voluntary written informed consent.
- 9) The patient is willing in the process of preparation and self-administration of the study drug.

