Women of childbearing potential (WOCBP) are considered those women who have menarche and until becoming post-menopausal unless permanently sterilised. Permanent sterilisation methods include hysterectomy, bilateral salpingectomy, and bilateral oophorectomy. A postmenopausal state is defined as no menses for 12 months without an alternative cause.

Two or more of the following methods are acceptable and must include one barrier method:

- Surgical sterilisation (i.e. bilateral tubal removal, bilateral ovary removal, hysterectomy for female partners; vasectomy for males)
- Placement of an intrauterine device or intrauterine system
- Hormonal contraception associated with the inhibition of ovulation (implantable, patch, oral)
- Barrier methods (for male patients, this must be a condom; for female patients, either their partner's use of a condom or the patient's use of an occlusive cap [diaphragm or cervical/vault caps] with spermicidal foam/gel/film/cream/suppository). Barrier methods must be used in conjunction with another method.

Alternatively, true abstinence is acceptable when consistent with the patient's preferred and usual lifestyle. If a patient is usually not sexually active but becomes active during the course of study, they and their partner should use two of the contraceptive methods listed above. Any female patient who becomes pregnant during the course of the trial will be withdrawn from the trial unless she consents to a termination of the pregnancy.

Male patients who have been sterilised are required to use one barrier method of contraception (condom).

4.6.1. *Exposure of partners during the study*

There is a risk of drug exposure through ejaculate (which also applies to vasectomised males) which might be harmful to the sexual partners, including pregnant partners, of male patients. Barrier contraception should be used throughout the study and for 90 days after the last day of IMP administration.

Fathering a child through samples before IMP exposure is acceptable. Similarly, a surrogacy through frozen eggs collected before IMP exposure is acceptable i.e. prior to previous study participation.

4.6.2. *Sperm Donation*

Male patients should not donate sperm for the duration of the study and for at least 90 days after the last day of IMP administration.

4.6.3. *Egg Donation*

Female patients should not donate eggs whilst on the study and for at least 90 days after the last day of IMP administration.

4.6.4. *Breast Feeding*

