5.4 Trial procedures**5.4.1 Screening**

Patients considered unsuitable for inclusion in this trial should be identified by their Investigator before the end of their participation in the preceding trial (i.e. should the investigator feel participation in the long term safety study is not in the patient's benefit or if the patient declines to participate in AK581) allowing adequate time for any alternative therapy to be implemented. The Investigators should discuss the suitability of patients to enter AK581 with the Sponsor at least four weeks before the likely time of entry in order that documentation, including ICF, can be put in place and continuity of drug supply can be ensured.

Ideally the patient will be entered on the long term safety trial on the last day of dosing of the parent trial on condition that they have provided consent.

5.4.2 *Dosing period(s)*

Patients will be dispensed drug at suitable timepoints during the trial

5.4.3 *Exiting the trial*

Patients may choose to leave the trial at any time or may be withdrawn by the Investigator in case of lack of efficacy, adverse reactions to rVA576 (Coversin), lack of compliance or for any other reason which, in the opinion of the Investigator, makes their continued participation no longer in their best interests.

Patients will also leave this trial, or an extended access trial if one is required, once rVA576 (Coversin) is fully approved and reimbursed for their indication in their country and once continuity of supply has been ensured.

5.4.4 *End of Study/Follow-up*

All patients will have a follow up clinic visit at 1 Month \pm 7 days and all women of child bearing potential (WOCBP) will have a follow up visit at Month 3 \pm 7 days from last dose.

Table 8: Schedule of Events for PNH Patients

EVENT (PNH)	Entry	ⁱ 1 Months (±7 days)	2 Months (±7 days)	3 Months (±7 days)	6 Months (±7 days)	9 Months (±7 days)	12 Months (±7 days)	15 Months (±7 days)	18 Months (±7 days)	21 Months (±7 days)	24 Months (±7 days)
Medical History. Eligibility & Informed Consent & demographics	✓										
ⁱⁱⁱ Physical Examination if not done within 7 days of entry	✓	✓	✓	✓	✓	✓	✓	✓	✓	✓	✓
^{iv} Vital Signs (including weight) at every visit	✓ ^{vii}	✓	✓	✓	✓	✓	✓	✓	✓	✓	✓
^v ECG	✓ ^{vii}						✓				✓
Urinalysis (including pregnancy testing) ^{viii}	✓ ^{vii}	✓	✓	✓	✓	✓	✓	✓	✓	✓	✓
ⁱⁱ Haematology & Chemistry including LDH, FBC and creatinine (local or central labs)	✓ ^{vii}	✓	✓	✓	✓	✓	✓	✓	✓	✓	✓

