AE and Concomitant Medication reporting	✓	✓	✓	✓	✓	✓	✓	✓	✓	✓
MAVE Assessment	✓	✓	✓	✓	✓	✓	✓	✓		✓

Table 8 Notes (for PNH patients):

- i. Investigator visits may take place more frequently if needed or desired (unscheduled visits/testing where needed), but the schedule shown is the minimum permitted
- ii. All blood draws will be taken pre-dose. If not possible, a note to that effect must be made in the medical records and captured in the eCRFs
- iii. Physical Examination - Inclusive of vein assessment and injection site inspection
- iv. Vital Signs – Diastolic and Systolic blood pressure & pulse rate
- v. Patients must complete the Quality of Life (QOL) Instruments and sponsor non-validated questionnaire at every clinic visit
- vi. Drug accountability will be performed at each visit. Patients are requested to bring in empty vials only and inform the site of unused vials remaining in their fridge.
- vii. Test to be conducted at entry if not done within 14 days of entry visit.
- viii. Pregnancy tests for women of childbearing potential must be done monthly. The current protocol design requires a pregnancy test at each hospital visit and then every 3 months after Month 3 (Months 1, 2, 3, 6, 9, 12, 15, 18, 21, 24, 27, 30, 33, 36, 39, 42, 45, 48 & ET). In addition Home Pregnancy tests must be repeated every month during the use of rVA576 (Coversin) and up to 90 days after the last dose of rVA576 (Coversin) by the patient.
- ix. Total LDH and LDH isoenzymes via a central laboratory maybe required as per the schedule to monitor patient safety (unscheduled visit/test is also permitted)
- x. All patients will have a follow up clinic visit at 1 Month ± 7 days in addition all women of childbearing potential (WCBP) will have a follow up visit at Month 3 ± 7 days from last dose whereby urine pregnancy test will be conducted on site.
- xi. Routine ECG to be performed at entry and then annually during the study. (*Limb lead or 12 lead ECG machines are acceptable*)

FLAER/Flow Cytometry: Local lab or via Central Lab (if not available locally). A 7 day window is permitted for each visit.

Table 9: Schedule of Events for aHUS patients

EVENT (aHUS)	Entry	ⁱ 1 Months (±7 days)	2 Months (±7 days)	3 Months (±7 days)	6 Months (±7 days)	9 Months (±7 days)	12 Months (±7 days)	15 Months (±7 days)	18 Months (±7 days)	21 Months (±7 days)	24 Months (±7 days)
Medical History, Eligibility, Informed Consent & demographics	✓										

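### Inclusion criterion 4 treats any 12 months of amenorrhoea as not of childbearing potential, whereas section 4.6 also requires that there be no alternative cause

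*Protocol*

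**What the plan says.** Criterion 4 (protocol synopsis and section 4.1) requires WOCBP to agree to contraception and to have a negative pregnancy test at screening. It then says who is outside that group: "Women are considered post-menopausal and not of childbearing potential if they have had 12 months of amenorrhea". It adds that women are "considered sterile if they have had surgical bilateral oophorectomy (with or without hysterectomy) or tubal ligation at least six weeks previously".

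Section 4.6 (Contraception) defines the same group differently: "A postmenopausal state is defined as no menses for 12 months without an alternative cause". On surgery it says: "Permanent sterilisation methods include hysterectomy, bilateral salpingectomy, and bilateral oophorectomy".

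Several procedures depend on the classification. Note viii to Tables 8 and 9, and section 5.7.7, state: "Pregnancy tests for women of childbearing potential must be done monthly". Section 5.4.4 provides that "all women of child bearing potential (WOCBP) will have a follow up visit at Month 3", and the follow-up notes to both tables repeat this. The urinalysis list in section 5.7.8 gives hCG for WOCBP only.

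Two places are worded more broadly. The follow-up column header in Tables 8 and 9 attaches the 3-month visit to females, and SAP section 3.4.4 lists urinalysis hCG for female patients. Neither mentions childbearing potential.

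**The concern.** The two definitions can give opposite answers for the same woman, and no text says which one governs. Eligibility is judged on criterion 4, which is the looser of the two.

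Section 4.6 itself accepts intrauterine systems and "Hormonal contraception associated with the inhibition of ovulation (implantable, patch, oral"). If one of these suppresses menses for a year, which is a clinical assumption rather than something the documents state, the user meets criterion 4's test for being post-menopausal while still fertile. Amenorrhoea from illness would have the same effect.

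What is at stake is pregnancy surveillance. Section 7.2.4 contraindicates the drug in pregnancy and requires it to be stopped on a positive test unless the patient consents to a termination. Section 4.6 says the segment 2 and 3 reproductive studies are still to be done. Monthly testing keeps the gap between tests to about a month. Without it, detection waits until someone suspects pregnancy or the investigator chooses to test.

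**Working it through.** The plan gives no figure to reproduce. The check is a comparison of text, followed by a count of the tests involved.

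**1. Classification under each definition**

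| Woman | Criterion 4 | Section 4.6 |
|---|---|---|
| 12 months without menses, no other cause | Not WOCBP | Not WOCBP |
| 12 months without menses, other cause | Not WOCBP | WOCBP |
| Bilateral oophorectomy at least six weeks ago | Sterile | Permanently sterilised |
| Hysterectomy alone | Not named; qualifies after 12 months without menses | Permanently sterilised |
| Bilateral salpingectomy | Not named | Permanently sterilised |
| Tubal ligation at least six weeks ago | Sterile | Not named; list is open |

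The second row is a direct conflict, and it runs in the unsafe direction. The surgical rows are weaker. Section 4.6 introduces its list with *include*, so tubal ligation is unaddressed there rather than ruled out. Leaving salpingectomy out of criterion 4 errs towards more testing.

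**2. What the second-row woman is not required to have under criterion 4**

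- On any reading: the negative screening test as an entry condition, the criterion 4 contraception agreement, and the monthly home tests (section 5.7.7; note viii).
- On the WOCBP-only reading (sections 5.4.4 and 5.7.8; table notes): also the clinic urine hCG and the Month 3 visit.
- On the broader reading (follow-up header in Tables 8 and 9; SAP 3.4.4): she keeps the clinic hCG and the Month 3 visit.

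**3. Count per misclassified woman, assuming she completes 48 months**

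Scheduled on-drug visits are Months 1, 2 and 3 (3 visits) plus Months 6 to 48 every three months, (48 − 6)/3 + 1 = 15. The total is 3 + 15 = 18.

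- Home tests, upper: 48 monthly + 3 in the 90 days after the last dose = 51, taking them as additional to the clinic tests.
- Home tests, lower: only months with no clinic test, (48 − 18) + 1 (post-dose month 2) = 31.
- Clinic tests, upper: entry 1 + 18 + 1-month follow-up 1 + Month 3 follow-up 1 = 21.
- Clinic tests, lower: 20, if the entry test is carried over from the parent trial's last visit on the same day (section 5.8).

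Tests not required:

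- Broader reading: 31 to 51, all of them home tests.
- WOCBP-only reading: 20 + 31 = 51 to 21 + 51 = 72, plus one visit.

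Forty-eight months is the maximum duration (section 5.3), so shorter participation lowers every figure.

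**4. Size of the pool**

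The SAP introduction says no aHUS patients will enter, and SAP section 5 gives up to approximately 50 patients. Neither document says how many are women or how many have amenorrhoea from another cause.

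**The case against.** The best defence is that section 4.6 is the dedicated section, states positively who counts as WOCBP, and is the stricter text on amenorrhoea. A careful investigator reading both would probably apply it. That lowers the chance of misclassification, but criterion 4 is complete in itself, appears twice, and does not refer to section 4.6.

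A second defence is that protection against pregnancy does not rest on WOCBP status alone:

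- Section 4.6 requires highly effective contraception of all sexually active patients, with two methods including a barrier.
- Exclusion 5 bars pregnant women whatever their classification.
- Section 7.2.4 requires serum hCG when pregnancy is suspected.
- A woman amenorrhoeic because of hormonal contraception or an intrauterine system is already using an accepted method.

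All of this stands, and it confines the gap to routine testing, the criterion 4 agreement and possibly one visit. It does not close the gap, because exclusion 5 prescribes no test and section 7.2.4 acts only on suspicion.

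A reader might go further and infer that such a woman certainly loses every clinic hCG test and the Month 3 visit. The documents do not support that: the follow-up header and SAP 3.4.4 can be read as covering all females. A reader might also infer that the two sterility lists contradict each other. Because the section 4.6 list is open, that difference is mostly a matter of drafting.

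**Conclusion.** Criterion 4 is wrong as written, and the point is minor. It omits a condition that section 4.6 imposes, so a fertile woman with secondary amenorrhoea can be classed as not of childbearing potential and excused the screening test, the criterion 4 agreement and monthly testing. Whether she also loses the clinic hCG and the Month 3 visit depends on which of the conflicting statements a site follows.

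The size per woman is as counted above. It assumes that a site applies criterion 4 literally and that she stays the full 48 months. The number of such women is unknown and may be zero. Nothing here supports an inference that any patient has been harmed, or that an estimate, analysis set or sample size is affected: the analysis is descriptive and does not use childbearing status beyond a data listing.

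**What to change.** 1. In the synopsis and section 4.1, add *without an alternative cause* after the 12 months of amenorrhoea in criterion 4.
2. Have criterion 4 refer to section 4.6 for the definitions of WOCBP and of permanent sterilisation, so that one definition governs. The first edit needs this one: a hysterectomy is itself an alternative cause of amenorrhoea, and criterion 4 does not name hysterectomy alone, so the added phrase by itself would make those women WOCBP under criterion 4.
3. Do not extend criterion 4's six-week interval to hysterectomy or salpingectomy; neither section states one for them. Section 4.6 does not name tubal ligation, so if the sponsor wants it to count, that section must say so.
4. In Tables 8 and 9, align the follow-up column header with the WOCBP wording of the notes (for Table 8: "in addition all women of childbearing potential (WCBP) will have a follow up visit at Month 3") and of section 5.4.4.

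The cost is a few wording changes in the protocol. Any woman reclassified as WOCBP takes on the contraception agreement, the pregnancy tests and possibly one extra visit. On section 4.6's own definition, a woman with amenorrhoea from another cause should already have these.
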